Patient and Public Involvement

Materials used to communicate details of the study with patients and family members were developed with input from the Vanderbilt Community Advisory Council. Study authors will disseminate the results of this study online and via social media in forms suitable for public understanding.

Study Design

The DirEct Versus VIdeo LaryngosCopE (DEVICE) trial is a pragmatic, multicenter, unblinded, parallel-group, randomized trial comparing use of a video laryngoscope to use of a direct laryngoscope for the first attempt at emergency tracheal intubation among critically ill adults in the ED and ICU. The primary outcome is successful intubation on the first attempt. An

independent data and safety monitoring board (DSMB) is monitoring the progress and safety of the trial. Study institutions and investigators are listed in the supplementary file, section 2.

Study Population

The inclusion criteria for this study are:

- 1. Patient is located in a participating unit
- 2. Planned procedure is orotracheal intubation using a laryngoscope.
- 3. Planned operator is a clinician expected to routinely perform tracheal intubation in the participating unit.

The exclusion criteria for the study are:

- 1. Patient is known to be less than 18 years old
- 2. Patient is known to be pregnant.
- 3. Patient is known to be a prisoner.
- 4. Immediate need for tracheal intubation precludes safe performance of study procedures.
- Operator has determined that use of a video laryngoscope or use of a direct laryngoscope is required or contraindicated for the optimal care of the patient.

Randomization and Treatment Allocation

Patients are randomized in a 1:1 ratio to undergo intubation using a video laryngoscope or using a direct laryngoscope for the first attempt in permuted blocks of variable size, stratified by study site. Study-group assignments are generated using a computerized randomization sequence, placed in sequentially numbered opaque envelopes, and distributed to enrolling sites. Before opening the envelope, the operator determines that the patient meets eligibility criteria, records the predicted difficulty of intubation ("easy", "moderate", or "difficult") and selects the blade shape the operator plans to use if the patient is randomized to the video laryngoscope group ("hyperangulated" or "non-hyperangulated / standard geometry"). The

Study Interventions

Video Laryngoscope Group

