The minimum clinically important difference in successful intubation on the first attempt that would be needed to justify routine use of a video laryngoscope rather than a direct laryngoscope in the ED and ICU is uncertain. The current trial is designed to detect a 5% absolute difference between groups in the incidence of successful intubation on the first attempt. An absolute difference of 5% in successful intubation on the first attempt is similar to or smaller than the difference used in the design of prior airway management trials and is considered by airway management experts to be clinically meaningful. 21,28,38,39 Assuming (1) an incidence of successful intubation on the first attempt of 80% in the direct laryngoscope group, (2) 90% statistical power, (3) a two-sided alpha of 0.05, and (4) enrollment at 16 sites with an intra-cluster correlation for the primary outcome of 0.05, we calculated that detecting a 5% absolute increase in the incidence of successful intubation on the first attempt would require enrollment of 1,920 patients (960 per group). Anticipating missing data for up to 4% of enrolled patients, we will plan to enroll a total of 2,000 patients (1,000 per group).

Data and Safety Monitoring Board (DSMB) and Interim Analysis

A DSMB composed of experts with backgrounds in emergency medicine, pulmonary and critical care medicine, anesthesiology, bioethics, and biostatistics has overseen the design of the trial and is monitoring its conduct. The DSMB will review a single interim analysis prepared by the study biostatistician at the anticipated halfway point of the trial, after enrollment of 1,000 patients. The stopping boundary for efficacy was pre-specified as a P-value of 0.001 or less, using a chi-square test, for the difference in the incidence of the primary outcome between groups. This conservative Haybittle—Peto boundary was selected to allow the final analysis to be performed using an unchanged level of significance (P < 0.05). The DSMB retains the authority to stop the trial at any point, request additional data or interim analyses, or request modifications of the study protocol to protect patient safety. Trial safety monitoring and handling of adverse

events are described in detail in the supplementary file, section 5. Patient privacy and data storage details are listed in the supplementary file, section 6.

Statistical Analysis Principles

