Analyses will be conducted following reproducible research principles using R (R Foundation for Statistical Computing, Vienna, Austria).⁴⁰ We will present summary tabulations by treatment group. For categorical variables, the number and proportion of patients will be presented. For continuous variables, the mean and standard deviation or median and interquartile range will be presented, as appropriate.

We will analyze a single pre-specified primary outcome and a single pre-specified secondary outcome using a chi-square test. Consistent with recommendations of the Food and Drug Administration⁴¹ and the European Medicines Agency⁴², each will be tested using a two-sided P value with a significance level of 0.05. The primary analysis will occur in an intent-to-treat fashion among all patients randomized, excluding only those patients whose data was withdrawn from the study. For all other analyses except safety analyses, emphasis will be placed on the estimate of effect size with 95% confidence intervals, as recommended by the *International Committee of Medical Journal Editors*⁴³, and no corrections for multiple comparisons will be performed.

Main Analysis of the Primary Outcome

The main analysis will be an unadjusted, intention-to-treat comparison of successful intubation on the first attempt between patients randomized to the video laryngoscope group and patients randomized to the direct laryngoscope group, using a chi-square test. The difference in proportions, the associated 95% confidence interval, and a p value for the primary outcome will be presented.

Secondary Analyses of the Primary Outcome

Multivariable modeling to account for covariates

To account for relevant covariates, we will develop a generalized linear mixed effects model using a logit link function with the primary outcome as the dependent variable, study site as a random effect, and fixed effects of study group and the following pre-specified baseline covariates: age, sex, body-mass index, operator experience quantified as the operator's total number of prior intubations, and location of intubation (ED vs ICU). All continuous variables will be modeled assuming a nonlinear relationship to the outcome using restricted cubic splines with between 3 and 5 knots.

Effect Modification

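### The plan has an interim efficacy stop but no rule for estimation after it; if a true 5-point benefit triggers the stop, the plain difference averages about 9 points and its 95% interval covers the truth in about 78% of stopped trials

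*SAP*

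**What the plan says.** The SAP section on the DSMB and interim analysis plans one efficacy look "after enrollment of 1,000 patients". It sets the rule as follows: "The stopping boundary for efficacy was pre-specified as a P-value of 0.001 or less, using a chi-square test". Protocol section 9.4.5 says the same. Both documents justify the boundary only as leaving the final significance level unchanged.

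Under Main Analysis of the Primary Outcome, the SAP plans an unadjusted intention-to-treat comparison and says: "The difference in proportions, the associated 95% confidence interval, and a p value for the primary outcome will be presented". Protocol section 9.4.1 agrees. Neither text distinguishes a trial stopped at the interim from one that runs to 2,000 patients. Neither mentions an adjusted estimate, an interval matched to the boundary, or a caveat.

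On the size of effect, the SAP's Sample Size Estimation section says "The current trial is designed to detect a 5% absolute difference between groups". It also says that the difference needed to justify routine video use is uncertain.

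**The concern.** A trial that stops for efficacy at a strict boundary stops because its observed difference is large. The observed difference among stopped trials is therefore selected upward, and an interval that ignores the selection can miss a modest true effect more often than 5% of the time. Control of type I error does not correct this.

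It matters here because the plan leaves the clinically important difference open, so readers will weigh the size of the estimate as well as the P value. Protocol section 13 names early attainment of the objectives as a possible ground for termination, so this path is foreseen. Protocol section 9.4 labels analyses requested after enrollment as post hoc, so a qualifying interval not specified in advance would carry that label.

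**Working it through.** **Inputs**
- Interim size 1,000 (SAP, interim analysis). This is half of the planned 2,000, which reproduces as 1,920 / (1 − 0.04) = 2,000.
- "Patients are randomized in a 1:1 ratio" (SAP, Randomization), taken as 500 per arm.
- Boundary P ≤ 0.001, two-sided, z = 3.2905.
- Direct success: "an incidence of successful intubation on the first attempt of 80% in the direct laryngoscope group" (SAP, Sample Size Estimation).
- True benefit: the 5-point design difference, 80% against 85%.

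The plan states no figure for the estimate after a stop, so there is none to reproduce. The calculation treats patients as independent, as the chi-square test does.

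**Step 1: smallest difference that crosses.** The pooled chi-square crosses when d ≥ 3.2905 × √(p̄(1 − p̄) × 2/500), with p̄ = direct rate + d/2. With direct observed at 80%, p̄ = 0.8383 and the standard error is √(0.8383 × 0.1617 × 0.004) = 0.02328. So d = 3.2905 × 0.02328 = 0.0766, or 7.66 points. With continuity correction it is 7.84.

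| Direct rate observed | Smallest crossing difference (points) |
|---|---|
| 70% | 9.1 |
| 75% | 8.4 |
| 80% | 7.7 |
| 85% | 6.7 |
| 90% | 5.4 |

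**Step 2: what is reported, given a stop.** Both binomials were enumerated exactly at 500 per arm. Every outcome that crosses in favor of video was kept and weighted by its probability. The interval is the ordinary Wald 95% interval.

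| True rates | Chance of stop | Mean difference given stop (points) | Overstatement | 95% coverage given stop |
|---|---|---|---|---|
| 80% v 85% | 11.2% | 9.06 | +81% | 78% |
| 80% v 87% | 38% | 9.33 | +33% | 93% |
| 80% v 88% | 57% | 9.59 | +20% | 96% |
| 80% v 90% | 88% | 10.50 | +5% | 97% |
| 70% v 75% | 6.4% | 10.51 | +110% | 60% |
| 75% v 80% | 8.0% | 9.89 | +98% | 69% |
| 85% v 90% | 18% | 8.02 | +60% | 86% |

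For the first row, 9.06 / 5 = 1.81. A true 3-point benefit (80% v 83%) stops in 1.9% of trials, with a mean of 8.97 points and coverage of essentially zero.

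**Step 3: over both looks.** A two-look simulation (1,000,000 runs, 80% v 85%) gives a mean of 4.74 points in trials that continue. Weighting, 0.112 × 9.06 + 0.888 × 4.74 = 5.22 points, a bias of about +0.2. Overall 95% coverage is 94.2%.

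**Step 4: the interval that matches the boundary.** For an observed 80% v 89.1%, the standard error is √(0.80 × 0.20/500 + 0.891 × 0.109/500) = 2.27 points.
- 95%: 9.1 ± 1.96 × 2.27 gives 4.7 to 13.5.
- 99.9%: 9.1 ± 3.2905 × 2.27 gives 1.6 to 16.6.

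In the first row of Step 2, the 99.9% interval covers 5 points in 99.6% of stopped trials.

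**The case against.** The strongest reply is that nothing in the plan is wrong. The plain difference is the maximum-likelihood estimate, the boundary is offered only as protection of the significance level, and no passage claims an unbiased estimate after a stop. Over all trials the estimate is nearly unbiased, and where a stop is likely the distortion largely disappears. All of this stands. It limits the point to a gap in reporting on one path.

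Four stronger readings are tempting, and the documents do not support them.

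- A reader might infer that every early-stopped trial must report at least about 1.5 times the design difference, whatever the truth. The 7.7-point figure belongs to an observed direct rate of 80%. Protocol section 1 puts first-attempt failure at 10 to 20%, so success of 80 to 90% is within its own range, and there the threshold falls to 6.7 and then 5.4 points. With true rates of 85% and 90%, 46% of stopped trials report less than 7.7. At 90% and 95% the overstatement is 33% and coverage is 94%.
- A reader might infer that the boundary is the only way to stop at 1,000 patients. The DSMB may stop at any point for safety, and such a stop does not select for large benefit in this way. A stop favoring direct is also possible, and would need about 8.9 points with direct at 80%.
- A reader might infer that the SAP expressly prescribes the plain estimate after a stop. It does not; this follows from its having a single unconditional rule. The supplementary file is not available here, but the SAP cites it for other matters (such as outcome definitions, safety, privacy and protocol changes), not estimation.
- A reader might infer that a bias-adjusted estimate solves the problem. For an observed 9.1 points, an unconditional adjustment gives about 8.7. Conditional maximum likelihood gives about 6.1 there (cutoff 7.66, standard error 2.38), but about −8 at an observed 8.0. That would favor direct after P ≤ 0.001 for video.

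**Conclusion.** The point holds in limited form. The plan provides for an efficacy stop and has no rule for estimation after it. Under its own design values a stop occurs in about 11% of trials. The plain difference then averages 9.1 points against a true 5, and its 95% interval covers the truth in 78% rather than 95%.

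These figures assume 500 evaluable patients per arm, independent outcomes, a true direct rate of 80%, a chi-square without continuity correction and a true benefit of 5 points. With 480 per arm, or with continuity correction, the overstatement is about 85%. For a true 5 points the direction is the same at every direct rate examined.

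The significance level, the stopping rule and the completed-trial analysis are not in question. The SAP's 1,920 does not reproduce from its stated inputs (the usual formula gives 2,424), but that is a separate matter and none of the figures here use it. This is a worthwhile, inexpensive improvement and not a fault in the primary test.

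**What to change.** Add to Main Analysis of the Primary Outcome that, if the efficacy boundary is crossed at the interim, the report will give the 99.9% confidence interval matching the 0.001 boundary beside the plain difference and its 95% interval. The report will also state that the plain estimate is expected to be too large after an early stop for efficacy. Protocol section 9.4.1 can refer to this text.

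An unconditional bias-adjusted estimate may be added as an option, but it moves the figure little. The conditional maximum-likelihood estimate should be left out because it is unstable near the boundary.

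The cost is a short paragraph and a line or two of code, used only after an early efficacy stop. The price is a wider, less favorable interval in that report: in the worked example, 1.6 to 16.6 points beside 4.7 to 13.5. The text should be in place before the interim result is known.

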7.1 Data Collection

Data collected for the purposes of this study will come from three sources: [1] variables documented in the electronic health record as part of clinical care, [2] variables recorded by clinical staff's bedside observation during the intubation procedure, and [3] variables reported by the operator immediately following the intubation procedure. Data from the electronic medical record will be collected by trained study personnel (key study personnel) using a standardized electronic case report form. It is infeasible to have research staff present during each emergency tracheal intubation. Therefore, clinical staff not participating in the tracheal intubation procedure will collect data elements relevant to outcomes of emergency tracheal intubation using a standardized electronic case report form. These variables are readily available by bedside observation and do not require interaction with the patient but are not uniformly documented in the electronic health record (e.g., lowest oxygen saturation and lowest blood pressure from induction to two minutes after tracheal intubation). Immediately following the intubation procedure, the operators will record data elements known only to them (e.g., glottic view obtained during the procedure and visualization of gastric aspiration in the oropharynx). Operators and clinical staff observing the procedure at the bedside will not be considered key study personnel. Training will be provided to clinicians who may serve as operators or bedside observers. The activities of these clinicians will be limited to the reporting of data routinely reported as part of clinical care.

The following variables will be recorded:

Baseline:

- age
- sex
- race and ethnicity
- height
- weight
- body mass index
- Acute Physiology and Chronic Health Evaluation (APACHE II) score
- active medical problems at the time of enrollment
- comorbidities
- indication for intubation
- vasopressor receipt in the hour prior to enrollment
- highest FiO2 in the hour prior to enrollment
- lowest SpO2/FIO2 ratio (or PaO2/FIO2 ratio) in the hour prior to enrollment
- Glasgow Coma Scale score
- oxygen delivery device at enrollment
- assessment of the likelihood of a difficult intubation
- presence of difficult airway characteristics
 - limited mouth opening
 - limited anatomic neck mobility
 - cervical immobilization due to trauma
 - increased neck circumference
 - \circ facial trauma
 - obesity

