9.4.2 Secondary Analyses

We will perform:

- 1. Intention-to-treat comparisons of secondary, exploratory, and safety outcomes; and
- 2. Intention-to-treat comparison of the primary outcome between groups using a generalized linear mixed effects model including a random effect for site and fixed effects for group assignment and pre-specified baseline variables, including: age; sex; body mass index; and location at enrollment (ED or ICU).

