- 4. Operator's pre-enrollment assessment of the anticipated difficulty of intubation (Easy; Moderate; Difficult; Not Recorded). We hypothesize that the operator's pre-enrollment assessment will modify the effect of study group assignment on the primary outcome, with a greater increase in the incidence of successful intubation on the first attempt with use of a video laryngoscope compared with a direct laryngoscope among patients assessed as Difficult or Moderate compared to Easy. This hypothesis of effect modification is supported by significant effect modification in a meta-analysis of multiple prior randomized trials.⁹
- 5. Operator experience at the time of enrollment.
 - 1. Total number of previous intubations performed by operator. We hypothesize that the total number of previous intubations performed by the operator will modify the effect of study group assignment on the primary outcome, with a greater increase in the incidence of successful intubation on the first attempt with use of a video laryngoscope compared with a direct laryngoscope among operators with fewer previous intubations compared to operators with a greater number of previous intubations. This hypothesis of effect modification is supported by significant

effect modification observed in a prior randomized trial among critically ill adults, but differs from a meta-analysis including trials of intubation in the operating room that did not observe effect modification based on the operator's prior experience. 9,28

2. Proportion of previous intubations performed by the operator using a direct laryngoscope. We hypothesize that the proportion of previous intubations performed by the operator using a direct laryngoscope will modify the effect of study group assignment on the primary outcome, with a greater increase in the incidence of successful intubation on the first attempt with use of a video laryngoscope compared with a direct laryngoscope among operators with a lower proportion of previous intubations performed by the operator using a direct laryngoscope compared to operators with a higher proportion of previous intubations performed by the operator using a direct laryngoscope.

We will also perform an effect modification analysis for the primary outcome that includes a three-way interaction between study group, total number of previous intubations performed by the operator, and proportion of previous intubations performed by the operator using a direct laryngoscope.

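### The secondary adjusted model for first-attempt success leaves out the operator's pre-envelope difficulty rating, so no planned overall estimate allows for chance imbalance in anticipated airway difficulty; the gain from adding it is modest

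*SAP*

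**What the plan says.** The SAP's main analysis is an unadjusted chi-square comparison. Under Secondary Analyses of the Primary Outcome it adds a logit-link mixed model with site as a random effect and, besides study group, these fixed effects: "age, sex, body-mass index, operator experience quantified as the operator's total number of prior intubations, and location of intubation (ED vs ICU". Protocol 9.4.2 has a shorter list: "age; sex; body mass index; and location at enrollment (ED or ICU". Neither list contains predicted difficulty, and neither document gives a reason.

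The rating is a baseline variable. Under Randomization and Treatment Allocation the SAP states: "Before opening the envelope, the operator determines that the patient meets eligibility criteria, records the predicted difficulty of intubation". Protocol 7.1 lists among its baseline data "assessment of the likelihood of a difficult intubation".

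The SAP uses the rating once, as item 4 under Effect Modification: "Operator's pre-enrollment assessment of the anticipated difficulty of intubation (Easy; Moderate; Difficult; Not Recorded". It expects a larger benefit of video laryngoscopy "among patients assessed as Difficult or Moderate compared to Easy". That model holds the rating's main effect and its interaction with group. Handling of Missing Data plans multiple imputation for missing covariates in adjusted analyses. Randomization is stratified by site only.

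**The concern.** The adjusted model is there to take account of relevant covariates. Apart from body mass index, nothing in it describes the airway, although a three-level airway rating is collected before allocation is known. In an unblinded trial that timing matters. The operator's form on difficult-airway features is completed after the procedure and includes what was seen during it.

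Being an effect modifier is no reason for leaving a variable out. Location, body mass index and total prior intubations are all on the modifier list and are all covariates too.

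At stake is how well the adjusted analysis answers one obvious question: did the arms differ by chance in anticipated difficulty, and does the overall effect hold once that is allowed for? As planned, the only model that contains difficulty yields effects within difficulty categories, not an overall effect.

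**Working it through.** **The plan's own figure.** The documents give no figure for the adjusted analysis. The nearest is the sample size: 80% vs 85%, two-sided alpha 0.05, 90% power, 960 per group. The usual formula is n = [1.96·√(2·p̄·(1−p̄)) + 1.2816·√(p1(1−p1) + p2(1−p2))]² / δ². With p̄ = 0.825 this is (1.96·√0.28875 + 1.2816·√0.2875)² / 0.05² ≈ 1,212 per group. At 960 per group, power is 82.3%. The stated 960 is therefore not reproduced. That is a separate matter; it is noted here because the baseline power below is 82 to 84%, not 90%.

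**Assumptions.** The documents give neither the mix of ratings nor success by rating. Assumed: Easy / Moderate / Difficult 45 / 40 / 15%, direct-arm success averaging 80%, and a constant odds ratio set to give 85% overall in the video arm. There were 960 patients per group and 3,000 simulated trials per scenario, with no site effect and no other covariates.

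**How much the rating could explain.** Share of direct-arm outcome variance = Σ w(p − 0.80)² / (0.80 × 0.20). Moderate case: (0.45×0.08² + 0.40×0.03² + 0.15×0.16²) / 0.16 = 0.00708 / 0.16 = 4.4%. The weak case gives 0.65% and the strong case 10.6%.

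**Simulated results, without and then with the rating**

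| | Weak | Moderate | Strong |
|---|---|---|---|
| Direct-arm success by rating (%) | 83 / 79 / 73.7 | 88 / 77 / 64 | 93 / 74 / 57 |
| Fall in variance, standardised risk difference | 0.4% | 4.5% | 9.6% |
| Log odds ratio | 0.354 → 0.357 | 0.348 → 0.363 | 0.348 → 0.385 |
| Its standard error | 0.1213 → 0.1218 | 0.1213 → 0.1240 | 0.1214 → 0.1278 |
| Estimate / standard error | 2.92 → 2.93 | 2.87 → 2.93 | 2.87 → 3.01 |
| Power | 83.7% → 83.9% | 81.8% → 83.7% | 81.5% → 85.7% |
| SD of shift in risk difference removed (points) | 0.15 | 0.35 | 0.53 |

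Compare within columns. Each power figure has a simulation error of about √(0.84×0.16/3,000) = 0.7 points, so differences between columns in unadjusted power carry no meaning.

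On the log-odds scale the standard error rises. Power improves because the conditional log odds ratio grows proportionately more.

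**Chance imbalance.** With 1,000 per arm, the SD of the between-arm difference in a 15% category is √(2×0.15×0.85/1,000) = 1.6 points. In the moderate case, success among the other 85% is (0.45×0.88 + 0.40×0.77)/0.85 = 82.8%, against 64% for Difficult. A one-SD imbalance then moves the risk difference by 0.016 × 18.8 ≈ 0.30 points. The estimate's own SD is about 1.7 points.

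**The case against.** The strongest reply is that this is a preference about one covariate in a secondary model. The confirmatory test is unadjusted. The SAP puts the weight of its other analyses, safety aside, on effect sizes and confidence intervals, so no trial decision turns on this model's p value. The interval for the unadjusted difference already allows for chance imbalance on average, and at about 1,000 per arm that imbalance is small. Difficulty is not ignored either: odds ratios within each category will be reported. Body mass index, operator experience and site are in the model and may carry some of the same information, and the increment over that fuller model has not been computed. The rating also has a Not Recorded category, so including it needs a rule.

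All of this stands as a limit on size. It does not explain the omission. Category-specific odds ratios are not an overall adjusted estimate, and other modifiers were given both roles.

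A reader might also infer that the SAP itself treats the rating as a strong predictor of success. It does not. Its statement is "We hypothesize that the operator's pre-enrollment assessment will modify the effect of study group assignment on the primary outcome", which concerns the treatment effect. A variable can modify an effect without being strongly prognostic, and no passage ranks the rating above other predictors.

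**Conclusion.** The omission is real and worth correcting, but the benefit is modest. Adding the rating would give the adjusted test about 0 to 4 points of power, or a standardised risk difference about 0 to 10% less variance. Both ranges rest on assumed success rates and an assumed mix of ratings. Both are upper-end, because the comparison was with no adjustment rather than with the SAP's existing covariates. At the weak end the gain is negligible.

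Three stronger readings are not supported:

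- **That precision is lost for free.** Under the planned logit link, the standard error of the log odds ratio rises slightly. The variance reduction belongs to a standardised risk difference, which the SAP does not plan.
- **That the gain can be counted as patients saved.** The sample size serves the unadjusted test, whose power does not change.
- **That the primary result is at risk.** It is an unadjusted chi-square comparison and is untouched.

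**What to change.** Add predicted difficulty (Easy / Moderate / Difficult) as a fixed effect in the adjusted model, in the SAP and in Protocol 9.4.2. The two covariate lists already differ, since only the SAP includes operator experience, so they can be aligned in the same edit.

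State that Not Recorded values are handled by the multiple imputation already planned for covariates. Reconcile this with item 4 under Effect Modification, where Not Recorded is a category of its own.

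Preferably, also report a standardised risk difference with its 95% confidence interval beside the odds ratio. It is on the same scale as the main analysis, and it is where any gain in precision would appear.

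The change should be made before enrollment is complete. Protocol 9.4 labels additional analyses requested after that point as post hoc.

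The cost is two degrees of freedom and one rule for unrecorded values. No new data are needed, and the primary test, interim analysis and sample size stay as they are.
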